The investigation will be reported to the Scientific Ethics Committees, Danish Medicines Agency and Danish Data Protection Agency. The participants in the investigation are assured access to receive further information about the project through the coordinating investigator, who as contact person is referred to in the participant information. The "Rights of Trial Subjects" published by the Scientific Ethics Committee will be provided. The trial will be considered as having started on the date when there is a signed declaration of consent from the first patient, who will thereby be considered as included. The trial will be considered ended when the last patient has had the post-operative interview and the CRF for this patient is completed. At the end of the trial, investigator and sponsor will inform the Scientific Ethics Committee and the Danish Medicines Agency of this within 90 days. The trial will be registered in an international database (www.clinicaltrials.gov), before the recruitment of patients is started.

Data collection and storage:

Primary investigator will arrange for data collection and storage of CRFs in locked premises. The study will be reported to the Data Protection Agency. Data will be stored for 5 years after conclusion of the trial. The information about the patients' health conditions, other purely private circumstances and other information that arises in connection with the trial is covered by the obligation of confidentiality. The information about the patients is protected by the Act on processing of personal information and the Danish Health Act.

Responsible department:

Department of Anaesthesiology, Herlev Hospital, [name], legally represented by sponsor and primary investigator [name]

Economy:

The sponsor and primary investigator has taken initiative to the biomedical research project.

The project budget covers:

1) salary for subinvestigator

459.000 DKK

2) expenses including GCP course, BIS monitoring electrodes and BIS monitor

60.000 DKK

3) fees at the Danish Medicines Agency and The National Committee on Health Research Ethics

15.000 DKK

4) expenses to project medicine (Sugammadex)

80.000 DKK (applied for from the MISP committee)

Total budget 640.000 DKK

Financial support (640.000 DKK = 113.790 USD) for the project has been applied for via the pharmaceutical company MSD, Glostrup to the international MSD MISP program. MSD is lending TOF-Watch for use for the study.

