part of the procedure as well as the total procedure time, and reduce the number of recurrences by long term follow-up.

Purpose:

The purpose of this study is to investigate surgical work space and surgical conditions in patients scheduled for laparoscopic umbilical, -linea alba and incisional herniotomy. The patients will act as their own control with evaluation of surgical work space and surgical conditions during both deep NMB and no NMB.

Hypothesis:

Deep NMB defined as TOF=0 and post-tetanic count (PTC) ≥ 1 , will give better surgical workspace, better surgical conditions, as well as shorter duration of surgery and reduced number of recurrences of hernias compared with no NMB.

Method:

See appendix 1, flow diagram.

Design:

Randomized, cross-over design, with blinding of patient and surgeon. Randomization is used to determine the treatment sequence (no NMB followed by deep NMB (Group A) or deep NMB followed by no NMB (Group B)) in order to blind the surgeon.

Outcomes:

Primary outcome:

Improvement of surgical workspace (rated on a 5-point scale) estimated as the difference between the workspace during deep NMB and the workspace without NMB. Ratings are performed in the same patient during stable pneumoperitoneum at 12 mmHg.

Protocol
The hernia study
September 16. 2016

Secondary outcomes: (comparing Group A with Group B)

- Surgeon's rating of surgical conditions while suturing the hernia (5-point rating scale)
- Duration of operating time (from first incision to last suture)
- Assessments if the surgical space is better, unchanged or worse when evaluating before and after the intervention
- Number of sudden contractions of the abdominal wall during operation (bucking or coughing),
- Number of insufflator alarms where pneumoperitoneum > 17 mmHg,
- Number of episodes with continuous abdominal contractions where the abdomen feels "tight" but the operation can still proceed (the intestines are gradually displaced near the inner surface of the abdominal wall).
- Number of recurrences of hernias by 2 year follow-up (separate publication). Patients will 2 years after operation receive a letter with invitation to ambulatory clinical assessment by a surgeon at Herlev Hospital or have the opportunity to receive a visit by a surgeon at their home address.

Number of patients:

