34 eligible patients allocated into an assessor-blinded randomized cross-over design: one group first receives deep NMB followed by no NMB and the other group first receives no NMB followed by deep NMB.

Protocol
The hernia study
September 16. 2016

Groups:

Group A: After intubation and placement of trocars: Bolus of saline (placebo) 6 ml. After three minutes the surgeon assesses the surgical workspace with pneumoperitoneum 12 mmHg. Bolus of rocuronium 0,6 mg/kg When TOF=0 the surgical workspace is assessed again.

Group B: After intubation and placement of trocars: Bolus of rocuronium 0.6 mg/kg When TOF=0 the surgeon assesses the surgical workspace with pneumoperitoneum 12 mmHg. Sugammadex is administered and when TOF=100% the surgical workspace is assessed again[8].

Criteria for participation:

Inclusion criteria:

Patients \geq 18 years old

Elective laparoscopic umbilical herniotomy, incisional herniotomy and linea alba herniotomy.

Can read and understand Danish

Informed consent

Exclusion criteria:

Known allergy to sugammadex, rocuronium or mivacurium

Known homozygous variants in the butyrylcholinesterase gene

Protocol
The hernia study
September 16. 2016

Severe renal disease, defined by S-creatinine > 0.200 mmol/L, GFR < 30ml/min or hemodialysis)

Neuromuscular disease that may interfere with neuromuscular data

Lactating or pregnant (Women of child bearing potential must take a urine pregnancy test at the day of the operation. The test will be provided by the hospital staff).

Indication for rapid sequence induction

Withdrawal criteria:

- In case of cancelling the operation, the patient will not receive the intervention. Data will not be available and therefore not analyzed and the patient will be considered as a "dropout".
- In case of the patient not receiving the intervention (trial medicine/placebo) after randomization, the data will not be analyzed and the patient will be considered as a "dropout".

These "dropout" patients will be disclaimed further data analysis.

Major violation:

- In case of need for increasing pneumoperitoneum to > 12 mmHg due to poor surgical conditions
- Converting to laparotomy

These will be characterized as major violations. The data will be analyzed in the intention-to-treat analysis, but excluded from the per-protocol analysis.

End of study:

When 34 patients have been evaluated considering the primary endpoint according to the intention-to-treat analysis, the study is finished.

Patient information:

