Neuromuscular monitoring will be done with TOF-Watch SX connected to a computer for collection of neuromuscular data (Version 2.5 INT 2007, Organon, The Netherlands). The monitoring will be done according to international research guidelines [9]. TOF-Watch SX will be placed on the arm, where there is the least monitoring in general. The skin over the ulnar nerve will be washed with spirits and rubbed with a piece of gauze. Small ECG electrodes will be used. They are placed on the wrist over the ulnar nerve. The

Protocol
The hernia study
September 16. 2016

acceleration transducer is placed on the thumb and attached in the associated hand adaptor. TOF-Watch SX will be started. It will be calibrated (CAL2), when the patient does not react to verbal command and TOF mode will be started. Measurements will be taken every 15 sec. When stable neuromuscular monitoring during 2 minutes is assured, rocuronium will be given. When TOF=0, PTC will be measured every 3 min., and rocuronium/saline infusion is adjusted in accordance with randomization. The hand with TOF-Watch and apparatus is covered. The readings from the TOF-Watch are seen on the connected computer by nurse anesthetist and investigator. Intravenous cannula is placed in the opposite hand.

Anesthesia:

General anesthesia with induction of propofol 2 mg/kg and remifentanil 1.0 mcg/kg/min. Tracheal intubation is performed no less than 3 minutes after induction of anesthesia making sure that the patient has received at least 3 mcg/kg remifentanil [10;11]. Anesthesia will be maintained with propofol 3 mg/kg/hour and remifentanil 0.25-0.5 mcg/kg/min, and adjusted according to depth of anesthesia under guidance of BIS (Entropy GE Healthcare).

Treatment values:

Blood pressure: Mean artery pressure (MAP) max. 30 % difference from baseline
BIS 40-60.

Medicine according to intervention: (see appendix 1)

Group A:

Bolus of saline 6 mL (placebo) before first assessment followed by bolus rocuronium 0.6 mg/kg ideal body weight (IBW) and rocuronium infusion to target level TOF=0 and PCT ≥ 1

Group B:

Rocuronium 0.6 mg/kg IBW before first assessment followed by sugammadex according to level of NMB and saline infusion (placebo).

Both groups:

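### Sudden contractions are compared between Group A and Group B over a window that, as written, includes time under the opposite block condition

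*Combined protocol and SAP*

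**What the plan says.** The outcome list in the protocol is headed "Secondary outcomes: (comparing Group A with Group B". It includes "Number of sudden contractions of the abdominal wall during operation (bucking or coughing" and "Duration of operating time (from first incision to last suture". Insufflator alarms and episodes of a tight abdomen are on the same list, with no stated window.

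Under Design, the two sequences are "no NMB followed by deep NMB (Group A) or deep NMB followed by no NMB (Group B". Under Groups, A starts "After intubation and placement of trocars: Bolus of saline (placebo) 6 ml" and B starts "After intubation and placement of trocars: Bolus of rocuronium 0.6 mg/kg". The switch in A is a rocuronium bolus. For B, "Sugammadex is administered and when TOF=100% the surgical workspace is assessed again". Before that, both groups have had "General anesthesia with induction of propofol 2 mg/kg and remifentanil 1.0 mcg/kg/min" (Anesthesia section), with no relaxant until after the trocars are in.

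Under Medicine according to intervention, A then goes on with a rocuronium infusion and B with a saline infusion. The Data collection section asks for a single number of sudden contractions. It does not divide that number by block condition or by time.

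**The concern.** The hypothesis is about deep NMB against no NMB. The sequence label matches that contrast only from the second intervention onward. Before it, the match is broken in three ways:

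- From incision to trocar placement nobody is blocked. This is the opposite condition for A but not for B.
- During its saline phase and until rocuronium takes effect, A is still unblocked.
- During its first assessment, and until reversal is complete, B is deeply blocked.

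If deep NMB reduces contractions, some no-block events are credited to the deep group, and some deep-block time lowers the count in the no-block group. Both errors pull the comparison toward no difference, in a trial with only about 17 patients per group. A null result on this count could then be read as evidence that deep NMB has no effect, when part of it comes from the window. Alarms and tight episodes may share the problem.

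**Working it through.** **The plan's own figure.** Sample size inputs (Sample size calculation): difference 1, SD 2, alpha 0.05 (taken as two-sided), power 0.80. The normal approximation gives ((1.960 + 0.842) × 2 / 1)² = 31.4, so 32. The paired t-test gives 33.4, so 34. The stated 34 reproduces. It belongs to the within-patient primary outcome, where each condition is rated separately, and is not affected here. Allocation is 1:1 (Randomization), so 34 / 2 = 17 per group.

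**Time under the opposite condition.** From the Surgical conditions section: one rating 3 minutes after the first intervention and one 3 minutes after the second. Assumed: 5 minutes from incision to trocars, rocuronium onset *o* and reversal *r* each 0 to 3 minutes, and the same onset in both groups because drug and dose are the same.

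- Group A, unblocked: 5 + 3 + *o* = 8 to 11 minutes.
- Group B, deeply blocked: (3 − *o*) + *r* = 0 to 6 minutes.

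The two are linked through *o*. The corner cases (A, B) are (8, 3), (11, 3), (8, 6) and (11, 0).

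**Observed ratio.** With operation length *L*, opposite-condition minutes *a* and *b*, true rate ratio R = 0.50 and a constant event rate:

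observed ratio = [a + (L − a)R] / [(L − b) + bR]

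| L (min) | (8, 3) | (11, 3) | (8, 6) | (11, 0) | Range |
|---|---|---|---|---|---|
| 90 | 49/88.5 = 0.554 | 50.5/88.5 = 0.571 | 49/87 = 0.563 | 50.5/90 = 0.561 | 0.55-0.57 |
| 60 | 34/58.5 = 0.581 | 35.5/58.5 = 0.607 | 34/57 = 0.596 | 35.5/60 = 0.592 | 0.58-0.61 |
| 45 | 26.5/43.5 = 0.609 | 28/43.5 = 0.644 | 26.5/42 = 0.631 | 28/45 = 0.622 | 0.61-0.64 |

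**Power.** Simulated with 17 per group, Poisson counts with gamma frailty (shape 2), Mann-Whitney test, two-sided 0.05, R = 0.50 and an assumed mean of 4 contractions without NMB. With no mixing, power is about 0.48.

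| L (min) | Whole window |
|---|---|
| 90 | 0.33-0.38 |
| 60 | 0.29-0.34 |
| 45 | 0.23-0.28 |

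Counting from the second rating gives about 0.44 to 0.47 across the three lengths. That window drops the first 5 + 3 + 3 = 11 minutes: 11/90 = 12% to 11/45 = 24% of the operation.

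**Operating time.** On the Surgical conditions timing, both groups wait 3 + 3 minutes, so the scheduled waits cancel in A minus B. On the Groups timing, A waits 3 minutes plus onset and B waits onset plus reversal, so A minus B = 3 − reversal. For an assumed reversal of 1 to 5 minutes this is +2 to −2 minutes.

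**The case against.** The strongest reply is that the window is undefined rather than wrong. The Surgical conditions section describes both workspace ratings first, and then uses the same phrase about the operation for the ratings made while suturing. On that usage the contraction count might already start after the second intervention. The case report form itself and the flow diagram in appendix 1 are not available here and could settle it. This stands as a possible reading. But neither the outcome definition nor the data-collection item restricts the count, and the plain sense of the phrase is the whole operation.

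Second, every input to the size except the two 3-minute waits and the 17 per group is assumed, including a constant event rate through trocar placement, waiting and suturing. That also stands. With no mixing at all, power is only about 0.48 (0.36 at an assumed mean of 2), so a null result would be weak evidence in any case.

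Third, counting from the second rating does not give a clean contrast. Rescue for poor conditions is saline in A and mivacurium in B, each followed by a three-minute wait. Block can therefore re-enter B's later window. This is correct, and the analysis has to allow for it.

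**Conclusion.** The point holds for the contraction count and may extend to alarms and tight episodes. On the plain reading, the comparison of A with B mixes block conditions and understates any reduction under deep NMB. Under the stated assumptions a true ratio of 0.50 reads 0.55 to 0.64, depending on operation length, and some of an already low power is lost. It concerns secondary outcomes only.

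A reader might go further in three ways that the documents do not support:

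- **Operating time is biased.** It does span both phases, but the scheduled waits are equal on one timing and differ by at most about 2 minutes either way on the other, under assumed reversal times. No direction is shown, and total time matches the stated interest in total procedure time.
- **The dilution could be larger.** Pairing the longest exposure in each group (11 and 6 minutes) gives 28/42 = 0.67 at 45 minutes. That needs rocuronium onset of 3 minutes in A and 0 in B, with the same drug and dose.
- **The later window isolates the block condition.** Rescue mivacurium in B means that it does not.

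**What to change.** For the comparison of A with B, count contractions, insufflator alarms and tight episodes from the second workspace rating to the last suture. List earlier events separately by phase. Report rescue boluses by group and flag events that follow one. Keep operating time as declared. Time from the second rating to the last suture may be added as a supplementary measure, but not described as attributable to block condition alone.

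Where counts already collected cannot be split, keep the whole-window count, give the split count as a sensitivity analysis in the patients who have it, and state that the whole-window contrast is probably understated.

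The cost is one clock time and a split tally on the case report form, plus wording. No patients or procedures are added. The surgeon already makes the second rating, so blinding is not affected. There are two downsides. Under the assumptions above, 12 to 24% of the window is no longer counted. And the text is dated September 2016 while inclusion was planned for February 2015 to February 2017, so split counts may be missing for many patients.

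Separately, the Groups section ties most workspace ratings to the train-of-four response, while the Surgical conditions section sets them at three minutes after each intervention. These passages must be reconciled, because the second rating would become the start of the count.

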Postoperative pain treatment with paracetamol, NSAID and morphine according to local guidelines.

PONV profylaxis:

I.v. dexamethason 8 mg routinely

Data collection

Perioperative data collection that will be noted in CRF:

Type of operation with operation code

Batch-number, expiration date, used and surplus quantities of rocuronium and sugammadex, TOF values (NMB sheet)

Body temperature measured immediately after intubation and again immediately before extubation

Size of hernia defect measured during operation just before the defect is sutured

Surgical ratings on 5 point scale

Operating time (from first incision to last suture)

Number of sudden abdominal contractions and episodes with “tight” abdomen

Need for additional NMB to optimize surgical conditions

Postoperative registration:

Number of patients with recurrences of hernias 2 years after herniotomy.

Statistics:

Eligible patients and excluded patients will be registered at a screening list.

Data from all randomized patients, who receive the intervention, will be included in the intention-to-treat analysis.

Patients, included in the intention-to-treat analysis, but who are categorized as major violation, will be excluded from the per-protocol analysis.

Normal distributed variables will be expressed by means and standard deviation; variables that are not normal distributed will be expressed by medians and interquartile range and the Mann-Whitney U test used for comparison of the median values.

Fisher's exact test will be used at comparisons of percentages. A p value < 0.05 is considered significant.

As the study is a crossover trial, it is necessary to test for a possible period effect and a treatment period interaction. To detect a possible period effect a two sample t test to compare the differences between the periods in the two groups of patients will be carried out. If there is no general tendency for patients to do better in one of the periods, we assume that the mean differences between the periods to be of the same size but with opposite signs.

To investigate the possibility of a treatment-period interaction a two sample t test will be carried out by noticing, that in the absence of an interaction, the patients response to the treatment will be the same regardless of the order in which it is received.

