If there is no period effect and no treatment-period interaction the analysis of the data regarding the primary outcome will be done by performing a Wilcoxon signed-rank sum test on all 34 patient's data (differences in workspace between the two treatments).

Primary outcome:

Improvement of surgical workspace estimated as the difference between the workspace (rated on a 5-point scale) during deep NMB and the workspace without NMB. Ratings are performed in the same patient during stable pneumoperitoneum at 12 mmHg.

Sample size calculation:

With a clinical relevant decrease of surgical workspace of 1 on the rating scale, an expected standard deviation of 2, type 1 error 0.05 and power 0.80, we calculated the sample size of 34 patients in total.

Up to 50 patients can be included to have an evaluable primary outcome in 34 patients.

Risks, side-effects and events:

Sugammadex: According to the Danish Medicine Agency's product summary, the side effects are as follows:

Very common (> 10%)	Taste disturbances.
Common (1-10%)	Anesthesia complication
Not common (0,1-1%)	Consciousness during anesthesia. Allergic reactions.

Laparoscopic herniotomy is done at Gentofte Hospital with an intraabdominal pressure at 12 mmHg without use of muscle relaxation for intubation and in some cases with use of bolus of muscle relaxation decided by the attending anesthetist. Patients allocated to group DEEP will receive rocuronium in a dose corresponding to a deep neuromuscular blockade (PTC < 8) after intubation. It is not regarded as a disadvantage to use large doses of muscle relaxation, since the effect is fully reversed by sugammadex at the end of surgery.

Registration of adverse events:

Patients will be observed during their stay at the hospital and will be contacted by telephone on first and seventh postoperative day. Possibly adverse events during this period will be reported. Finally the patient's case files will be reviewed for reports of adverse events at 17-21 days after operation.

The patients are encouraged to contact the local investigator, if they suspect any adverse events in connection with the trial and are treated according to applicable clinical principles and guidelines in the department.

Adverse events are registered as of the time when the patient is signing informed consent and the intravenous anesthetic is administered. All events are followed up until the final diagnosis or cause is established, and this is registered on the CRF.

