provided to any inspector. In the event the regulatory authority requests or requires any action to be taken to address any citations, Principal Investigator and Institution agree, after consultation with MSD, to take such action as necessary to address such citations.

F. A copy of all 15 Day Reports and Annual Progress Reports / Development Safety Update Report (DSUR) are to be submitted as required by the applicable regulatory authority by the Principal Investigator. Principal Investigator agrees to cross reference this submission according to local regulations, to the Study Drug number (IND, Clinical Study Authorization (CSA)/EudraCT approval number, etc) at the time of submission. Additionally Principal Investigator agrees to submit a copy of these reports to MSD (Attn: Global Safety; [contact]) at the time of submission to the appropriate regulatory agency.

G. MSD may provide the Principal Investigator and Institution, at Study initiation and on an ongoing basis, with information regarding the Study Drug, including but not limited to safety information. The Principal Investigator and Institution agree to hold this information in confidence.

H. Principal Investigator & Institution accept to follow the latest Executive Order on Good Clinical Practice for Clinical Trials involving Human Medicine (In Danish: Bekendtgørelse om god klinisk praksis i forbindelse med kliniske forsøg med lægemidler på mennesker").

Principal Investigator and Institution accept also to report the serious adverse reactions and unexpected non-serious adverse reactions discovered within 2 working days to MSD att: Pharmacovigilance by [contact].

Side effects/events that will *not* be registered:

In general, side effects and events that are typically seen in connection with the normal course of anesthesia and operation will not be registered and reported to the Danish Medicines Agency. In this protocol side effects/events (AE) will be defined in the form of expected changes in pulse and blood pressure as a result of the anesthesia. Pulse and blood pressure values (measured 3 repeated times within a 10-minute period) that deviate less than +/- 30% of the starting level will thus be accepted and not registered. Side effects/events that may be ascribed to the operation with certainty, for example, pain in the surgical wound or wound infection will not be registered. Side effects/events that with certainty have arisen as a result of the patient's postoperative treatment will

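### Two-year hernia recurrence rests on one voluntary assessment, with no file check for recurrence and no rule for recurrences already repaired, so events can be missed

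*Combined protocol and SAP*

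**What the plan says.** All places are in the combined protocol and SAP.

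- **Hypothesis:** deep block is expected to give a "reduced number of recurrences of hernias compared with no NMB".
- **Outcomes, secondary list:** "Number of recurrences of hernias by 2 year follow-up (separate publication", under a heading that compares Group A with Group B.
- **Same entry, method:** "Patients will 2 years after operation receive a letter with invitation to ambulatory clinical assessment by a surgeon at Herlev Hospital". As an alternative, they "have the opportunity to receive a visit by a surgeon at their home address".
- **Data collection, Postoperative registration:** "Number of patients with recurrences of hernias 2 years after herniotomy".
- **Registration of adverse events:** patients "will be contacted by telephone on first and seventh postoperative day". Then: "Finally the patient's case files will be reviewed for reports of adverse events at 17-21 days after operation".
- **Side effects/events that will not be registered:** the exclusions include "Side effects/events that may be ascribed to the operation with certainty". The same section later has the coordinating investigator review each subject's file after surgery to look for side effects, with no date given.
- **Statistics:** percentages are compared by Fisher's exact test at 0.05. The intention-to-treat population is all randomised patients who receive the intervention.

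No section gives a diagnostic definition of recurrence, a rule for one repaired before the visit, a reminder or telephone route for non-responders, or a rule for analysing patients who are not assessed.

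**The concern.** Two kinds of recurrence are exposed.

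The first is a recurrence in a patient who does not take up the invitation. That patient contributes nothing, even if a reoperation is recorded in the hospital file.

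The second is a recurrence repaired before the visit. Such a patient may have an intact abdominal wall at 24 months. Whether the patient then counts depends on how the assessing surgeon reads an unstated rule. Two teams following this text could classify the same patient differently.

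At stake is a benefit that the protocol names in its hypothesis and to which it assigns a separate paper. Few events can be expected in 34 patients, so each one lost matters to the reported rate.

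**Working it through.** **1. The plan's own figure.** The only sample size is 34 patients, for the workspace rating (difference 1, SD 2, type 1 error 0.05, power 0.80). It reproduces as a paired comparison with standardised difference 1/2 = 0.5: exact noncentral-t power is 0.795 at n = 33 and 0.808 at n = 34. It was not derived for recurrence. No recurrence rate, attendance rate or recurrence sample size is stated.

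**2. The two wordings side by side.**

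| | Secondary outcomes | Postoperative registration |
|---|---|---|
| Unit | recurrences | patients with recurrence |
| Time | by 2-year follow-up | 2 years after surgery |
| Repaired before the visit | not stated | not stated |

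**3. Could another procedure catch the missing events?**
- Telephone contact is planned for days 1 and 7 only.
- The dated file review is at 17-21 days and is for adverse events.
- The undated file review is for side effects.
- Safety registration leaves out events ascribed with certainty to the operation, so it is not a dependable second source.

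None of these is a search for recurrence.

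**4. Weight of one event.** Allocation is 1:1, so 34/2 = 17 per group if balanced. One event is 1/17 = 5.9 percentage points of a group's rate.

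**5. Fisher's exact test (two-sided assumed, as sidedness is not stated).** With k events in one group and none in the other, p = 2 × C(17,k)/C(34,k).
- k = 6: 2 × 12,376/1,344,904 = 0.018
- k = 5: 2 × 6,188/278,256 = 0.044
- k = 4: 2 × 2,380/46,376 = 0.103

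Against zero, 5 is the smallest count that reaches p < 0.05. Losing one event there costs significance, but the direction stays the same.

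**6. Expected counts, all rates assumed.** Counted events = 34 × true risk × (1 − share repaired and not counted) × attendance. Attendance is taken as unrelated to recurrence. The ranges are 25-50% repaired and not counted, and 60-80% attendance.
- Risk 10%: true 34 × 0.10 = 3.4. Counted from 3.4 × 0.50 × 0.60 = 1.0 to 3.4 × 0.75 × 0.80 = 2.0.
- Risk 20%: true 34 × 0.20 = 6.8. Counted from 6.8 × 0.50 × 0.60 = 2.0 to 6.8 × 0.75 × 0.80 = 4.1.

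**7. Unassessed patients.** The gap between best-case and worst-case overall risk is (number unassessed)/34: 3/34 = 8.8 points, 7/34 = 20.6 points.

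**8. Power with complete ascertainment.** Fisher's test, 17 per group, assumed risks: about 5% for 20% versus 10%, and about 19% for 30% versus 10%.

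**The case against.** The strongest reply is that the text is less defective than it looks.

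- **The timing words.** A reader might infer that the two sections contradict each other, one cumulative and one a status at 2 years. The documents do not support that firmly. The Background also speaks of reducing recurrences *by* long-term follow-up, where the word can simply mean *at* follow-up. A patient with a repaired recurrence can still be listed among patients with recurrence. What stands is the difference in unit and the absence of a rule.
- **History-taking.** The plan specifies a clinical assessment by a surgeon, which may well include asking about interim repair. It would be too strong to say that repaired recurrences are removed. What stands is that nothing requires the question or says how to count the answer.
- **Attendance.** The home visit should reduce non-attendance. It remains voluntary and does nothing to settle how repaired recurrences count.
- **Bias between groups.** A reader might infer that one sequence would look falsely better. That needs early repair or non-attendance to differ by group, and the documents show no mechanism for this. The Blinding section intends patients to stay unaware of allocation through recurrence follow-up, although Ethical considerations mentions routine unblinding after the operation.
- **Relevance.** Recurrence is the last-listed secondary outcome, reserved for a separate paper, and the comparison has little power in any case. This is true and limits the weight of the point. Low power does not justify losing events that a simple check would find.

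**Conclusion.** The point holds as a gap in ascertainment. Followed as written, the plan misses recurrences in patients who do not attend and does not ensure that recurrences already repaired are counted.

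Its size cannot be fixed from the documents. Each missed event is 5.9 percentage points with 17 per group. Under the assumed ranges, 3.4-6.8 true recurrences would shrink to about 1.0-4.1 counted.

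The Fisher example shows sensitivity at the threshold only. A reader might infer that one missed event would reverse a result, but 4 versus 0 points the same way as 5 versus 0, and 6 versus 0 would survive the loss of one event. That fragility also comes mainly from the small groups.

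The primary outcome is unaffected. The change is worth making because recurrence is a named hypothesis and the remedy is cheap. It will not turn the comparison into a well-powered one.

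**What to change.** 1. In both Secondary outcomes and Postoperative registration, define the outcome as the number of patients with any recurrence from surgery to 2 years, found on assessment or shown by a documented reoperation for recurrence at the index site.
2. Require the 2-year assessment to ask about interim repair.
3. At 2 years, check the hospital file of every patient in the intention-to-treat population, whether or not they attend, within the consent given.
4. Count a documented interim reoperation as a recurrence whatever the 2-year assessment shows.
5. Report, by group, how many patients were assessed and by which source (clinic, home or file only).

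The cost is amended wording and one file review per patient: 34, or up to 50 under the inclusion ceiling in Sample size calculation. In non-attenders, the review finds only recurrences known to the hospital. The consent pages are not available here, so the investigators should confirm that a file check at 2 years is covered.
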